9.4.2 Primary Endpoint

Complete Remission

CR will be determined by the investigator per the modified IWG MDS criteria (Cheson 2006). Per the IWG MDS criteria responses must last at least 4 weeks. Instructions for the assessment of IWG response including the provision of a 2-week window for unscheduled hematology evaluations to meet the IWG criteria of CR are provided in Section 8.1.1.

The CR will be evaluated in the Intent-to-Treat (ITT) population. CR rate and 95% exact binomial confidence intervals (CIs) will be calculated by treatment group. Patients who do not have any post-baseline response assessment will be considered as non-responders and will be included in the denominator. The stratified Cochran–Mantel–Haenszel (CMH) test will be applied to compare the CR rates between the 2 treatment groups, stratified by IPSS-R risk group (Intermediate, High, and Very High Risk) and by geographical region (North America, Western Europe, and Israel versus Eastern Europe). The final analysis of CR is planned for the time when all 190 patients have completed the Cycle 7 Day 1 response assessment or discontinued treatment, whichever comes first. Patients with missing response assessment data will be considered as a failure to achieve CR, including patients who have died, withdrew consent, or started a new treatment prior to achieving a CR.

The point estimate of the difference of the proportions for CR rate between the 2 treatment groups will also be provided along with 95% CI.

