6 INVESTIGATIONAL PLAN

6.1 Overall Study Design

This is a Phase 3, multi-center, randomized, double-blind, placebo-controlled study comparing the activity of tamibarotene plus azacitidine to placebo plus azacitidine as first-line therapy in retinoic acid receptor alpha (RARA)-positive participants with newly diagnosed higher-risk MDS (HR-MDS). Enrollment in countries in North America, Europe, and Israel is planned.

At the Pre-screening Visit, blood samples will be collected and sent to the Almac Diagnostics Laboratory for assessment of RARA biomarker to determine study eligibility. Pre-screening assessments for the RARA biomarker will be performed within 45 days of Cycle 1 Day 1, and screening assessments for all other eligibility criteria will be performed within 30 days of Cycle 1 Day 1.

Approximately CCI HR-MDS participants will be screened, with approximately participants randomized in the study. Participants will be randomized 2:1 to receive either tamibarotene plus azacitidine or placebo plus azacitidine. Randomization will be stratified by the Revised International Prognostic Scoring System (IPSS-R) risk group (Intermediate, High, and Very High Risk) and by geographical region (North America, Western Europe, plus Israel, and Eastern Europe).

Response will be assessed by the investigator per the modified International Working Group (IWG) MDS criteria (Cheson 2006). Bone marrow aspirates will be collected to measure response on Day 1 of Cycles 2 and 4, followed by every third cycle (7, 10, 13, etc.), with bone marrow aspirates collected at other times as clinically determined based upon clinical findings or changes in peripheral blood counts. Following the response assessment on Day 1 of Cycle 7, those in CR may have the frequency of bone marrow aspirates for response assessment reduced to every 6 cycles.

Participants will undergo response and safety evaluations throughout their study participation as detailed in the protocol Schedule of Activities (Section 1.3 in the study protocol). Participants may continue to receive study drug until experiencing an unacceptable toxicity, disease progression (including transformation into acute myeloid leukemia [AML]), relapse, decision to pursue post-remission therapy (such as HSCT) or an alternative anticancer therapy, participant withdraws consent, or the investigator determines it is in the best interest of the participant to discontinue study drug.

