6.4 Efficacy and Safety Endpoints

Unless otherwise specified, all efficacy and safety endpoints will use participants' all available data up to the data cut-off.

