6.4.1 Efficacy Endpoints

6.4.1.1 Primary Efficacy Endpoint and Estimand

The primary efficacy endpoint is CR defined as CR achieved by Cycle 7 Day 1, as determined by the investigator per the modified IWG MDS criteria (Cheson 2006). Peripheral blood counts to support the achievement of CR must be in the absence of transfusions or growth factors within the previous 7 days. The CR should be confirmed at least 4 weeks from the date of marrow sampling. Instructions for the assessment of IWG response including the provision of a 2-week window after the response assessment bone marrow aspiration for unscheduled hematology evaluations to meet the IWG criteria of CR are provided in the Study SY-1425-301 protocol, Section 8.1.1. The calculation of the rate of CR for each treatment group is:

CR rate (%) = number of *CR* responders achieved by Cycle 7 Day 1 / number of participants in the modified Intent-to-Treat (mITT) analysis set \times 100. The denominator is the mITT population in each treatment group.

Non-CR responders (mITT – CR responders) are participants who do not achieve CR or meet any of the following criteria:

Version 4.0

- 1. Do not have any post-baseline response assessments.
- 2. All response assessment results are missing or not done.
- 3. Discontinue prior to having a post-baseline assessment.
- 4. Withdraw consent before achieving a response.
- 5. Die before achieving a response.
- 6. Start a new anticancer therapy before achieving a response.
- 7. Experience prolonged treatment interruption requiring permanent withdrawal of study drug before achieving a response.

Table 3Primary Estimand

		Esti	mand Categ	ory	
		Population		Intercurrent	Populatio
		(Based on	Variable/	Event;	n Level
Objective	Treatment	mITT)	Endpoint	Strategy	Summary

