7.4.3 Primary Efficacy Endpoint Analysis Methods

7.4.3.1 Primary Estimand Analysis for CR

The final analysis of CR is planned for the time when the first approximately **CCI** randomized participants out of the planned **CCI** participants have completed the Cycle 7 Day 1 response assessment or discontinued treatment, whichever comes first.

The primary endpoint is CR achieved by Cycle 7 Day 1, as determined by the investigator per the modified IWG MDS criteria (Cheson 2006). There is expected to be a high correlation between CR achieved by Cycle 7 Day 1 and CR achieved at any time (Silverman 2006; VIDAZA UPSI), and therefore, the same effect size and other design assumptions are justified in the hypothesis testing below. The objective is to demonstrate the superiority of tamibarotene plus azacitidine compared to placebo plus azacitidine in CR in RARA-positive newly diagnosed HR-MDS participants.

The null hypothesis (H₀) to be tested is:

In RARA-positive participants with newly diagnosed HR-MDS, CR rate for participants in the tamibarotene plus azacitidine treatment group is the same as the CR rate for participants in the placebo plus azacitidine treatment group.

The alternate hypothesis (H_A) to be tested is:

In RARA-positive participants with newly diagnosed HR-MDS, CR rate for participants in the tamibarotene plus azacitidine treatment group is higher than the CR rate for participants in the placebo plus azacitidine treatment group.

The following analyses will be conducted separately:

- [1] Primary analysis of primary estimand (investigator response in mITT analysis set)
- [2] Sensitivity analysis of primary estimand (investigator response in ITT analysis set)
- [3] Sensitivity analysis of primary estimand (investigator response in PP analysis set)

The CR rate and 95% exact binomial CIs based on the Clopper-Pearson exact method will be calculated by treatment group.

Confidential

Syros Pharmaceuticals, Inc. SY-1425-301

The CR rate will be analyzed using the Cochran-Mantel-Haenszel (CMH) test to compare the 2 treatment groups with a 1-sided 2.5% level of significance. The strata for the test will be those used for stratified randomization, with potential pooling of strata if there is insufficient information in any stratum; the pooling strategy is specified in Section 7.4.2. The point estimate of the difference of the proportions for CR rate between the 2 treatment groups will be provided along with its 95% CI.

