7.4.7 Statistical/Analytical Issues

7.4.7.1 Interim Analysis

There will be 2 planned interim futility analyses, 1 for the CR and 1 for OS, respectively; these will be non-binding and will be conducted by the IDMC. The IDMC may recommend terminating the study for unfavorable results at an interim analysis.

Interim Futility Analysis for CR

An interim futility analysis of the CR rate is planned when the 95th randomized participant has completed the Cycle 7 Day 1 assessment or discontinued treatment, whichever comes first. The study may be terminated at CR interim futility analysis, if the 1-sided p-value from the stratified CMH test comparing the CR rates (tamibarotene plus azacitidine treatment group versus placebo plus azacitidine treatment group) is CCI. The non-binding futility bound is derived using a Hwang-Shih-DeCani (HSD) spending function with gamma = -4 (Hwang 1990). Refer to Section 7.4.3 for a description of the analysis of the CR rate.

Interim Futility Analysis for OS

If the CR rate is statistically significant at the time of the primary efficacy analysis of the CR rates between the 2 treatment groups, an interim OS futility analysis will be conducted at the final CR analysis, which is when approximately **CC** information fraction (**C** of the total **CC** events) has been observed, and the boundary for OS will be updated based on actual observed information fractions at the interim. The study may be terminated at OS interim futility analysis if the 1-sided p-value from the stratified logrank test comparing the distribution of OS (tamibarotene plus azacitidine treatment group

versus placebo plus azacitidine treatment group) is **CCI**. The non-binding futility bound is derived using Lan-DeMets spending function. Refer to Section 7.4.4 for a description of the analysis of OS.

Table 16	Planned Stopping Boundaries for CR Futility Analysis and FA
----------	---

Endpoint	Look	IF	Number of Participants	Boundary (1-sided p-value)	Minimum Critical Difference of CR Rate at the Boundary
CR rate	Futility	0.5	CCI	CCI	0.0045
	FA	1	CCI	CCI	0.1349

Abbreviations: CR = complete remission; FA = final analysis; IF = information fraction.

Table 17	Planned Stopping	Boundaries for	OS Futility An	alysis and FA

Endpoint	Look	IF	Number of Events	Boundaries (1-sided p-value)	Approx. Observed Hazard Ratios at the Boundary
OS	Futility	0.249	CCI	CCI	1.261
	FA	1	CCI	CCI	0.78

Abbreviations: FA = final analysis; IF = information fraction; OS = overall survival

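### The ITT sensitivity analysis of CR has no timing or follow-up rule, so at the primary cut it can include participants not yet due at Cycle 7 Day 1

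*SAP*

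**What the plan says.** SAP Section 7.4.3.1 sets the final CR analysis for the time when the first approximately N randomized participants, out of a larger planned number, "have completed the Cycle 7 Day 1 response assessment or discontinued treatment, whichever comes first". N is redacted in the SAP. Protocol Section 9.4.2 places the same analysis "when all 190 patients have completed the Cycle 7 Day 1 response assessment or discontinued treatment". Nothing is required of participants randomized after the first N.

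The mITT set (SAP 7.2.1) is those first N. SAP 8.2.1 explains that it was added so that they would have about 6 months of follow-up at the CR analysis. The ITT set (SAP 7.2.2) is everyone randomized, with no minimum follow-up.

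SAP 7.4.3.1 then lists three analyses of CR by C7D1: the mITT primary analysis, a "Sensitivity analysis of primary estimand (investigator response in ITT analysis set", and a per-protocol one. None has separate timing. SAP 7.4.5.2 repeats the mITT and ITT pair for ORR. SAP 6.4 uses "all available data up to the data cut-off" unless otherwise specified.

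Two scoring rules bear on this. SAP 6.4.1.1 lists the non-CR categories, the first being participants who "Do not have any post-baseline response assessments"; that list is written for mITT. Protocol 9.4.2 scores missing response data as failure in ITT, but for a cut at which all 190 have reached C7D1 or discontinued.

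**The concern.** The estimand is CR by C7D1, about six 28-day cycles after the start of treatment. A participant randomized two months before the cut has not had the chance to meet it. The CMH test needs a yes or no for every participant in the set, and the only default on offer for someone without a CR is no. Being too recently enrolled is then scored in the same way as failing treatment.

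The plan handles immaturity elsewhere. The mITT set exists to guarantee follow-up, and SAP 7.4.5.7 holds EFS to the OS analysis. The ITT analysis of CR has neither protection. At stake is how the ITT rates, difference and confidence interval are read. They would be presented as a robustness check on the primary result, yet would partly reflect how fast participants were enrolled before the cut.

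**Working it through.** **Size of the mITT set.** The CR futility look is "when the 95th randomized participant has completed the Cycle 7 Day 1 assessment or discontinued treatment" (SAP 7.4.7.1), at a stated information fraction of 0.5. 95/0.5 = 190, which agrees with the protocol.

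**Check of the CR bound.** The test is "with a 1-sided 2.5% level of significance" with 2:1 allocation, so about 127 and 63 participants. The critical difference is 1.96 × √[p(1−p)(1/127 + 1/63)]. With a pooled rate p = 0.275 this is 1.96 × 0.0688 = 0.1349, the figure in SAP Table 16. The bound therefore implies a pooled CR rate of about 27.5% (unstratified approximation).

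**ITT must end well above 190.** SAP Table 17 gives a hazard ratio of 0.78 at the final OS boundary. Deaths = (1.96/ln 0.78)² / (2/9) = 62.2/0.222 ≈ 280 (266 to 295 allowing for rounding of 0.78). Each death is a separate participant, so ITT must eventually exceed mITT by at least 266 − 190 = 76. How many are randomized before the CR cut is not stated.

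**Dilution if CR timing is the same in both arms.** Let f be the share of ITT randomized after the mITT cohort, and g the share of their eventual C7D1 CRs already recorded at the cut. The ITT difference is the mature difference × [1 − f(1 − g)].

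Assumptions for the illustration:
- 4 to 15 participants a month are enrolled over 6 months (182 days), giving 24 to 90 later participants.
- 15%, 55% and 100% of CRs are recorded by C2D1, C4D1 and C7D1 (days 28, 84 and 168).
- The mature difference is 0.224. This is close to the bound scaled to an assumed 90% power: 0.1349 × 3.24/1.96 = 0.223.

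Then g = 0.15 × 56/182 + 0.55 × 84/182 + 1.00 × 14/182 = 0.377.

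| Later participants | ITT N | Factor | Difference | Unstratified z |
|---|---|---|---|---|
| 0 | 190 | 1.00 | 0.224 | 3.26 |
| 24 | 214 | (190 + 9.05)/214 = 0.93 | 0.208 | 3.29 |
| 90 | 280 | (190 + 33.9)/280 = 0.80 | 0.179 | 3.41 |

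The z column uses the pooled rate 0.275 × factor. It rises because the larger N outweighs the smaller difference.

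**Wider ranges.** With entry uniform over 168 days, g = a/3 + b/2, where a and b are the shares of CRs recorded by C2D1 and C4D1. For g = 0.15 / 0.28 / 0.45 the factors are:
- 30 later participants: 0.88 / 0.90 / 0.93
- 60: 0.80 / 0.83 / 0.87
- 100: 0.71 / 0.75 / 0.81
- 190: 0.58 / 0.64 / 0.73

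For assumed rates of 35% and 15%, power is 0.85 in mITT and 0.84 to 0.94 in ITT across these cases. Both arms are multiplied by the same factor, so the ratio of rates does not move.

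**If CR timing differs by arm.** Take rates of 35% and 17%, with 80% and 100% of tamibarotene CRs recorded by C2D1 and C4D1, against 0% and 20% on placebo. Then g is 0.8/3 + 1/2 = 0.767 and 0.2/2 = 0.10. The later participants show 0.35 × 0.767 − 0.17 × 0.10 = 0.25, against a mature 0.18. The direction can reverse.

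**The case against.** A reader might infer that everyone short of C7D1 is scored as a non-responder, that the treatment difference is diluted by construction, and that a true effect would be made to look fragile. The documents do not support any of the three.

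- **Scoring.** Marrow is assessed at C2D1 and C4D1, and data run to the cut-off, so a later participant already in CR is a responder. The SAP's non-responder list is written for mITT, and neither document says how an ITT participant still on treatment and not yet due at C7D1 is scored. Non-response is the default outcome of the rules, not a stated ITT rule.
- **Direction and size.** The effect is zero if nobody is randomized after the mITT cohort before the cut. It can reverse if CRs come much earlier on tamibarotene, and the protocol cites a rapid onset for the combination in AML. Reversal does need marked asymmetry. With rates of 35% and 15% and g = 0.283 on placebo, tamibarotene would need g = (0.20 + 0.15 × 0.283)/0.35 = 0.69.
- **Fragility.** The z statistic holds or rises in the illustration, and power is largely kept.

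The decision-making analysis is also protected: the alpha-controlled test uses mITT, the per-protocol set is drawn from mITT, and no hypothesis depends on the ITT result.

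All of this stands and limits the point. It leaves the gap itself: an analysis of CR by C7D1 in a set that can include people not yet due at C7D1, with no rule to exclude or defer them. The 4-week CR confirmation in SAP 6.4.1.1 would lower the credit for early CRs further.

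**Conclusion.** The point holds in a limited form. As written, the ITT CR rates at the primary cut would be too low in both arms for the stated endpoint if anyone is randomized after the mITT cohort and before the cut. With similar CR timing by arm, the absolute difference would shrink by about 7% to 20% for 24 to 90 later participants. The number of later participants, the CR rates, the 0.224 difference and the CR timing are all assumptions; the documents give none of them. The relative effect and the power change little, and the primary test is untouched. This is a problem for interpreting a sensitivity analysis, not a threat to the trial's conclusion. It is worth correcting because the remedy is short and the plan already defers EFS in the same way.

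**What to change.** In SAP 7.4.3.1 and 7.4.5.2, state that the ITT sensitivity analyses of CR and ORR are run at a later cut, once every randomized participant has completed the C7D1 assessment or discontinued treatment, and at the latest at the OS analysis. State that the non-responder rule of 6.4.1.1 applies to ITT in the same way. Label any ITT CR figure shown at the primary cut as immature. With complete follow-up f = 0, so the dilution factor is 1.00.

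Restricting ITT at the primary cut to participants who could have reached C7D1 is a weaker option. The cut is triggered when mITT reaches that point, so the restricted set would nearly recreate mITT and add little.

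The cost is a sentence or two in each section. The full ITT result comes later; the primary test, alpha and study conduct do not change.

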7.4.3.2 Supplementary Estimand Analysis for CR

The supplementary endpoint of CR is CR achieved at any time, as determined by the investigator per the modified IWG MDS criteria (Cheson 2006). The analysis will be performed using the same statistical methodologies as applied to the primary estimand for participants in the mITT Analysis Set as described in Section 7.4.3.1.

7.4.4 Key Secondary Efficacy Endpoint Analysis Methods

The key secondary endpoint is the OS, defined as the time from the date of randomization to the date of death from any cause. The objective is to demonstrate the superiority of tamibarotene plus azacitidine compared to placebo plus azacitidine in OS in RARA-positive newly diagnosed HR-MDS participants.

The final analysis of OS will occur when a total of CCI death events is reached, which is approximately 70 months following the enrollment of the first participant.

The H₀ to be tested is:

In RARA-positive participants with newly diagnosed HR-MDS, OS for participants in the tamibarotene plus azacitidine treatment group is the same as the OS for participants in the placebo plus azacitidine treatment group.

The H_A to be tested is:

In RARA-positive participants with newly diagnosed HR-MDS, OS for participants in the tamibarotene plus azacitidine treatment group is superior to the OS for participants in the placebo plus azacitidine treatment group.

The primary analyses of OS will be based on the ITT analysis set.

OS is defined as the time from the date of randomization to the date of death due to any cause. Participants who do not die at the time of a data cutoff date (interim and/or final) will be censored at the last date the participant is known to be alive or at the analysis cutoff date, whichever is earlier.

The distribution of OS will be estimated for each treatment group using Kaplan-Meier methodology and compared between the 2 treatment groups using the log-rank test stratified by IPSS-R risk group (Intermediate, High, and Very High Risk) and by geographical region (North America, Western Europe, plus Israel, and Eastern Europe) at 1-sided 2.5% significance level.

The hazard ratio and corresponding 95% CI between the 2 treatment groups will be estimated using the stratified Cox proportional hazards model with the same stratification factors that are used for the stratified log-rank test. For both the stratified log-rank test and the stratified Cox proportional hazards model, the strata will be those used for stratified randomization, with potential pooling of strata specified in Section 7.4.2.

The number and percentage of participants with an event or who were censored will be summarized by treatment group. OS will be displayed by Kaplan-Meier curves. The 25th percentile, median, and 75th percentile OS (along with corresponding 95% CIs) will also be presented. Landmark analyses (OS rates, 95% CI, and number of participants at risk) will occur at 12 and 24 months post first dose and will be analyzed using the Kaplan-Meier method. The CIs will be calculated using the method of Brookmeyer and Crowley (Brookmeyer 1982).

A by-participant listing of the derived efficacy data used for determining OS will be provided.

Event and censoring rules for OS are provided in Table 12.

Table 12Assignments for Event and Censoring Dates for Overall Survival
Analysis

Situation Number	Situation	Date of Death or Censoring	Outcome
1	Death during the study	Date of death	Event
2	Participant still alive at data cutoff / death occurred after data cutoff	Date of cutoff	Censored

before data cutoff to be alive	3	Participant lost to follow-up before data cutoff	Date of last known to be alive	Censored
--------------------------------	---	--	--------------------------------	----------

7.4.4.1 Sensitivity Analyses of the Key Secondary Endpoint

Sensitivity Analysis 1: OS analysis based on unstratified log-rank test.

The distribution of OS will be estimated for each treatment group using Kaplan-Meier methodology and compared between the 2 treatment groups using the unstratified logrank test at 1-sided 2.5% significance level.

The hazard ratio and corresponding 95% CI between the 2 treatment groups will be estimated using the Cox proportional hazards model with treatment only as covariate.

The number and percentage of participants with an event or who were censored will be summarized by treatment group. OS will be displayed by Kaplan-Meier curves. The 25th percentile, median, and 75th percentile OS (along with corresponding 95% CIs) will also be presented. Landmark analyses (OS rates, 95% CI, and number of participants at risk) will occur at 12 and 24 months post first dose and will be analyzed using the Kaplan-Meier method. The CIs will be calculated using the method of Brookmeyer and Crowley (Brookmeyer 1982).

Sensitivity Analysis 2: Violation of proportional hazard assumption.

If the proportional hazard assumption does not hold for the OS analysis, the restricted mean survival time (RMST) may be substituted as appropriate. RMST is the participant's life expectancy until time t and can be estimated nonparametrically by the area under the Kaplan-Meier curve up to time t (Tian 2020). Time t will be chosen at the 90th percentile of observed follow-up times (Tian 2020).

The estimated RMST difference in OS between treatment groups will be reported with 95% CIs. The SAS procedure RMSTREG will be used with a linear link function.

Sensitivity Analysis 3: Adjusting for post-study therapy.

A sensitivity analysis of OS will be performed using an inverse probability censored weighting (IPCW) method. Logistic regression will be used to identify the baseline clinical covariates, such as IPSS-R, age, baseline bone marrow blast, etc., that could potentially be confounding factors. A weighted cox regression model will be used by applying the resulting weights from the logistic regression (Watkins 2013).

To obtain a less biased estimate of treatment effect, an IPCW method will be performed for OS, adjusting for post-study therapy. To compensate for the impact of switching to another therapy, participants with similar characteristics to those participants that switched treatment will be identified and a higher weight will be assigned to the participants that stayed on treatment and a lower weight will be assigned to the participants receiving post study therapy.

To calculate these weights, the likelihood of remaining uncensored will be estimated by logistic regression. Specifically, 2 logistic regression models, one using only baseline covariates and the other using both baseline and time-dependent covariates, will be performed. The coefficient between these 2 estimated probabilities of switching will be used for the assigned weights. Subsequently, participants who switched will have a lower weight than participants that did not switch.

